## 4.7 Cocaine Infusions

### 4.7.1 Infusion Session 1 (Day -2)

Table 4-4 shows the series of activities that occur on the day of the screening cocaine infusion. The times are nominal times with a window of  $\pm 3$  minutes up to 30 minutes after each infusion otherwise they are  $\pm 5$  minutes.

For a participant to receive the first screening cocaine and saline infusions (Session 1 – Study Day -2), s/he must have a urine drug toxicology screen that is negative for drugs of abuse (except marijuana) at Day -3. The participant's semi supine blood pressure must be  $\leq 140$  mm Hg (systolic) and  $\leq 90$  mm Hg (diastolic), heart rate must be  $\leq 100$  beats per minute taken in the half-hour prior to receiving any cocaine infusion. If blood pressure is elevated, it may be repeated one time to determine if the participant meets these criteria to receive an infusion. The participant's ECG taken within 30 minutes prior to receiving any cocaine infusion must not have any clinically significant abnormal arrhythmia or interval changes. The screening infusions are to ensure that Participants are responsive to and safely tolerate the cocaine test doses. Only Participants who are able to distinguish between a 20 mg and 40 mg dose of cocaine i.v. will be randomized. The highest score on VAS for "HIGH" effect at the 5 or 10 minute time point after cocaine infusion will be used to discriminate those individuals who can discern the differences between the two cocaine doses.

Participants who cannot safely tolerate the cocaine test doses and/or are unable to distinguish between a 20 mg and 40 mg dose of cocaine i.v. will not be eligible for the study. These participants will stay overnight for observation and be discharged from the unit the next day after their vital signs are assessed by the PI.

**Table 4-4 Screening Cocaine Infusion (Session 1) Schedule of Activities**

Timepoint relative to start of first infusion	Timepoint relative to start of last infusion	HR, BP	ECG	VAS
-30 min	-30 min	X	X	X
-15 min	-15 min	X		
-10 min	-10 min			
Time 0	Time 0 20 mg cocaine i.v.	20 mg cocaine i.v.		
5 min	5 min	X	X	X
10 min	10 min	X	X	X
15 min	15 min	X	X	X
20 min	20 min	X		
25 min	25 min	X		
30 min	30 min	X	X	X
45 min	45 min	X	X	X
55 min	55 min	X		X
60 min	Time 0	Saline i.v.		
65 min	5 min	X	X	X
70 min	10 min	X	X	X
75 min	15 min	X	X	X
80 min	20 min	X		
85 min	25 min	X		
90 min	30 min	X	X	X
105 min	45 min	X	X	X

Timepoint relative to start of first infusion	Timepoint relative to start of last infusion	HR, BP	ECG	VAS
115 min	55 min	X		X
120 min	Time 0	40 mg cocaine i.v.		
125 min	5 min	X	X	X
130 min	10 min	X	X	X
135 min	15 min	X	X	X
140 min	20 min	X		
145 min	25 min	X		
150 min	30 min	X	X	X
165 min	45 min	X	X	X
180 min	60 min	X	X	X
210 min	90 min	X		
240 min	120 min	X		
270 min	150 min	X		
300 min	180 min	X		
330 min	210 min	X		
360 min	240 min	X	X	

## 4.7.2 Infusion Sessions 2-5

### 4.7.2.1 Infusion Session 2

The baseline infusion sessions (Sessions 2 and 3 – Study Days 1 and 2) provide cardiovascular effects, subjective responses, and PK data of cocaine in the absence of SXC-2023.

During each baseline infusion session, each session will administer both cocaine and saline in a randomized order. Sessions 2 and 3 are randomized independently of one another. The participant's semi-supine blood pressure must be  $\leq 140$  mm Hg (systolic) and  $\leq 90$  mm Hg (diastolic), heart rate must be  $\leq 100$  beats per minute taken 15 and 30 minutes prior to the first cocaine infusion. If blood pressure or heart rate is elevated, it may be repeated one time to determine if the participant meets these criteria to receive an infusion. The participant's ECG taken in the half-hour (-30 minutes) prior to receiving any cocaine infusion must not have any clinically significant abnormal arrhythmia or interval changes. The pregnancy test must be negative before infusion.

The schedule of activities for infusion sessions are shown in [Table 4-5](#).

**Table 4-5 Infusion Sessions 2-5 (Days 1, 2, 8 and 9) Schedule of Activities**

Timepoint relative to start of first infusion	Timepoint relative to start of most recent infusion	HR, BP	ECG	VAS	BSCS	Cocaine PK (Days 2 and 9 Only)	SXC-2023 / Placebo Admin (Day 8 and 9 Only)	SXC-2023 Blood PK (Days 9-11 Only)
-180 min	-180 min						X	X a
-135 min	-135 min							
-120 min	-120 min							X (1 hr) a
-60 min	-60 min							X (2 hr) a
-30 min	-30 min	X	X	X				
-15 min	-15 min	X						
-15 min	-15 min					X		
-10 min	-10 min							
-5 min	-5 min				X			X (~3 hr) a

Timepoint relative to start of first infusion	Timepoint relative to start of most recent infusion	HR, BP	ECG	VAS	BSCS	Cocaine PK (Days 2 and 9 Only)	SXC-2023 / Placebo Admin (Day 8 and 9 Only)	SXC-2023 Blood PK (Days 9-11 Only)
Time 0	Time 0	Saline or Cocaine i.v.						
5 min	5 min	X	X	X		X		
10 min	10 min	X	X	X				
15 min	15 min	X	X	X		X		
20 min	20 min	X						
25 min	25 min	X						
30 min	30 min	X	X	X		X		
45 min	45 min	X	X	X				
55 min	55 min	X		X				X (~4 hr) a
60 min	Time 0	Saline or Cocaine i.v.						
65 min	5 min	X	X	X		X		
70 min	10 min	X	X	X				
75 min	15 min	X	X	X		X		
80 min	20 min	X						
85 min	25 min	X						
90 min	30 min	X	X	X		X		
105 min	45 min	X		X				
120 min	60 min	X	X	X		X		
125 min	65 min				X			
150 min	90 min	X	X			X		
180 min	120 min	X	X			X		X (6 hr) a
210 min	150 min	X						
240 min	180 min	X				X		
270 min	210 min	X						
300 min	240 min	X	X					X (8 hr) a
480 min	420 min					X		
540 min	480 min							X (12 hr) a
720 min	660 min					X		
780 min	720 min							X (16 hr) a
21 hr	20 hr							X (24 hr) b
33 hr	32 hr							X (36 hr) b
45 hr	44 hr							X (48 hr) b

a Day 9 only.

b These PK samples will be collected on Days 10 and 11

This infusion session 2 is performed as described above, with participants receiving one infusion of 20 mg of cocaine and one infusion of saline (in a randomized order).

Participants will be monitored for safety (vital signs, ECG) and administered subjective assessments (VAS, BSCS) at the timepoints shown.

The times are nominal times with the following windows:

- PK blood draws:  $\pm 1$  minute up to 30 minutes after each infusion and  $\pm 5$  minutes at all other time points.
- ECG, vital signs, and subjective assessments:  $\pm 3$  minutes up to 30 minutes after each infusion and  $\pm 5$  minutes at all other time points.

ECG, then vital signs will be collected first when multiple assessments are scheduled at the same nominal time.

Continuous cardiac monitoring by telemetry will be performed from one hour prior to starting transfusions until 4 hours after the last infusion. Participants will be monitored for at least 1 hour after the cocaine infusion by study personnel and staff. Thereafter, study personnel will monitor participants and take vital signs at the times specified in [Table 4-5](#).

#### **4.7.2.2 Infusion Session 3 (Day 2)**

This infusion session is performed as described above, with participants receiving one infusion of 40 mg of cocaine and one infusion of saline (in a randomized order). The participant's semisupine blood pressure must be  $\leq 140$  mm Hg (systolic) and  $\leq 90$  mm Hg (diastolic), heart rate must be  $\leq 100$  beats per minute taken in the half-hour prior to receiving any cocaine infusion. If blood pressure or heart rate is elevated, it may be repeated one time to determine if the participant meets these criteria to receive an infusion. The participant's ECG taken in the half hour (-30 minutes) prior to receiving any cocaine infusion must not have any clinically significant abnormal arrhythmia or interval changes. Pregnancy test must be negative prior to infusion.

Blood is collected to assess the PK of cocaine, according to the schedule shown in [Table 4-5](#).

Continuous cardiac monitoring by telemetry from one hour prior to starting infusions until 4 hours after the last infusion. Participants will be monitored for at least 1 hour after the cocaine infusion by study personnel and staff. Thereafter, study personnel will monitor participants and take vital signs at the times specified in [Table 4-5](#).

#### **4.7.2.3 Infusion Session 4 (Day 8)**

The infusion session is performed as described previously; cocaine (20 mg) and saline will be administered in the same order in which they were administered during Session 2. The participant's semi-supine blood pressure must be  $\leq 140$  mm Hg (systolic) and  $\leq 90$  mm Hg (diastolic), heart rate must be  $\leq 100$  beats per minute taken in the half-hour prior to receiving any cocaine infusion. If blood pressure or heart rate is elevated, it may be repeated one time to determine if the participant meets these criteria to receive an infusion. The participant's ECG taken in the half-hour (-30 minutes) prior to receiving any cocaine infusion must not have any clinically significant abnormal arrhythmia or interval changes. Pregnancy test will be done and must be negative before infusion.

SXC-2023 will be administered three hours prior to the first cocaine/saline infusion of the day.

#### **4.7.2.4 Infusion Session 5 (Day 9)**

The infusion session is performed as described previously; cocaine (40 mg) and saline will be administered in the same order in which they were administered during Session 3. The participant's semi-supine blood pressure must be  $\leq 140$  mm Hg (systolic) and  $\leq 90$  mm Hg (diastolic), heart rate must be  $\leq 100$  beats per minute taken in the half-hour prior to receiving any cocaine infusion. If blood pressure or heart rate is elevated, it may be repeated one time to determine if the participant meets these criteria to receive an infusion. The participant's ECG taken in the half-hour (-30 minutes) prior to receiving any cocaine infusion must not have any clinically significant abnormal arrhythmia or interval changes. Pregnancy test must be negative before infusion.

SXC-2023 will be administered three hours prior to the first cocaine/saline infusion of the day. This is the last dose to be administered in this study.

The full PK sampling for SXC-2023 is performed at this infusion session (pre-dose and 1, 2, 3, 4, 6, 8, 12, 16, 24, 36, and 48 hours post-dose).

## **5. STUDY ENDPOINTS**

### **5.1 Primary Endpoints**

The primary endpoints are adverse events (AEs) and cardiovascular responses including HR, BP, and ECG (including QTcF).

#### **5.1.1 Adverse Events**

Adverse events (AEs) will be assessed daily. An AE is defined as any reaction, side effect, or untoward event that occurs during the course of the clinical trial, whether or not the event is considered related to the investigational product or clinically significant. Sources of information about adverse events include reports by the participant, concomitant medications, and clinically significant abnormal findings on physical examination, vital signs, ECG, BDI, BAI, and mental status assessments.

All AEs, recorded during the inpatient portion of the study regardless of severity, will be followed by study Investigator until satisfactory resolution. AEs must be reported up to the date of final follow-up following hospital discharge. At the follow-up phone call, AEs will be recorded and followed; they will be followed to resolution only if they are serious, or if the study Investigator assesses them to be clinically significant.

#### **5.1.2 Cardiovascular and Blood Pressure Assessments**

Before and after each i.v. infusion, the participant's physiologic responses will be closely monitored using repeated HR, BP, and ECG readings assessed in semi supine position.

During the Screening Infusion Session 1, BP and HR will be recorded at the following nominal time points relative to the first infusion of the day: -30, -15, 5, 10, 15, 20, 25, 30, 45, 55, 65, 70, 75, 80, 85, 90, 105, 115, 125, 130, 135, 140, 145, 150, 165, 180, 210, 240, 270, 300, 330 and 360 minutes. Out of range BP and HR collected during the first 180 minutes post-dose will be repeated if deemed necessary by an investigator. Continuous cardiac monitoring with telemetry will begin approximately 60 minutes before the first infusion and will end 4 hours after the last cocaine infusion. Twelve-lead ECG measurements will be recorded at -30 minutes and at 5, 10, 15, 30, 45, 65, 70, 75, 90, 105, 125, 130, 135, 150, 165, 180, and 360 minutes after the first infusion. Study personnel and staff will monitor participants for at least 1 hour after each infusion. Times for collection of ECG and vital signs are nominal times  $\pm$  3 minutes for the first 30 minutes after the infusion and  $\pm$  5 minutes at all other time points. ECG, then vital signs will be collected first when multiple assessments are scheduled at the same nominal time.

During the baseline and treatment infusions (Sessions 2 to 5), BP and HR will be recorded at the following time points relative to the first infusion of the day: -30, -15, 5, 10, 15, 20, 25, 30, 45, 55, 65, 70, 75, 80, 85, 90, 105, 120, 150, 180, 210, 240, 270, and 300 minutes. Out of range BP

and HR collected during the first 180 minutes post-dose will be repeated if deemed necessary by an investigator. Continuous cardiac monitoring with telemetry beginning approximately 60 minutes before the first infusion until 4 hours after the second infusion. Twelve-lead ECG measurements will be recorded at -30 minutes and at nominal 5, 10, 15, 30, 45, 65, 70, 75, 90, 120, 150, 180 and 300 minutes after the first infusion. Times for collection of ECG and vital signs are nominal times  $\pm 3$  minutes for the first 30 minutes after the infusion and  $\pm 5$  minutes at all other time points. ECG, then vital signs will be collected first when multiple assessments are scheduled at the same nominal time.

ECG measurements to be recorded on a CRF include HR, RR, PR, QRS, and QT interval. For data analysis the QT interval will be corrected using the method of Fridericia (1920) (QTcF).

## **5.2 Secondary Endpoints**

### **5.2.1 Safety**

#### **5.2.1.1 Clinical Laboratory Test**

##### **5.2.1.1.1 Hematology**

Blood will be collected with appropriate anticoagulant and tested for complete blood cell count (CBC) with differential (absolute and percent) and platelets. The laboratory performing these assessments will be either directly regulated by CAP or CLIA or indirectly according to CLIA guidelines. The laboratory will need to provide a copy of the current certification. Hematology will be performed during screening, intake, on Day 6, and at discharge.

##### **5.2.1.1.2 Clinical Chemistries**

Blood will be collected in serum separation Vacutainer™ tubes and serum separated according to standard procedures. Quantitative analysis will be performed for the following analytes: glucose, blood urea nitrogen, creatinine, total protein, albumin, bilirubin, alkaline phosphatase, AST, ALT, calcium, sodium, potassium, chloride, and carbon dioxide. The laboratory performing these assessments will be either directly regulated by CAP or CLIA or indirectly according to CLIA guidelines. The laboratory will need to provide a copy of the current certification. Blood chemistries will be performed at screening, intake, on Day 6, and at discharge.

##### **5.2.1.1.3 Urinalysis**

A dipstick urinalysis test will be performed during screening, intake, Day 6, and at discharge.

### **5.2.2 Pharmacokinetics (PK)**

PK samples will be assayed for cocaine, BE, and SXC-2023 (as appropriate) using validated bioanalytical methods of liquid chromatography with tandem mass spectrometry (LC-MS/MS). For details of sample collection, processing, and shipment to the bioanalytical laboratory see the study Manual of Procedures (MOP). Approximately 179 mL blood will be collected for PK analysis and other clinical tests ([Appendix A](#)).

### **5.2.2.1 Cocaine and BE**

Blood samples (4 mL) will be collected during infusion Sessions 3 (Day 2) and 5 (Day 9) at predose (approximately 15 minutes before the first infusion) and at 5, 15, 30, 65, 75, 90, 120, 150, and 180 minutes, and at 4, 8, and 12 hours after the first infusion. Samples will be collected for assessment of cocaine and BE PK in 4-mL Vacutainer™ tubes containing K2EDTA.

### **5.2.2.2 SXC-2023 Blood PK**

On Day 9, blood samples will be collected approximately 15 minutes prior to the morning dose and 1, 2, 3, 4, 6, 8, 12, 16, 24, 36, and 48 hours post-dose. Samples for collection of SXC-2023 PK will be collected in 4-mL Vacutainer™ tubes containing sodium heparin.

## **5.2.3 Subjective Effects**

### **5.2.3.1 Brief Substance Craving Scale (BSCS)**

The BSCS is a self-administered assessment that asks the participant to rate his or her craving for cocaine. The BSCS used for this study is a modification of the State of Feelings and Cravings Questionnaire. Participants will use an electronic patient reported outcomes (ePRO) system provided by Technical Resources International, Inc, to answer BSCS. BSCS will be administered at pre-infusion and 125 minutes after the start of the cocaine infusion.

### **5.2.3.2 Columbia Suicide Severity Rating Scale (C-SSRS)**

The C-SSRS is a measure of suicidal ideation and behavior. At Screening, the “Baseline” version will be administered; on Days -3 and 12 and at the Follow-up visit (Days 19 to 26), the “Since Last Visit” version will be administered.

### **5.2.3.3 Subjective Response – Visual Assessment Scale (VAS)**

The VAS is a self-administered assessment evaluating the subjective effects of cocaine. Participants will use an ePRO system provided by Technical Resources International, Inc., to answer VAS. The participant should be instructed to respond to the questions with regards to how they feel at the moment of the assessment on a 100 mm Likert Scale with 0 being “Not at all” and 100 being “Extremely”. For the VAS, participants will report the degree to which they feel “any effects”, “high”, “good effects”, “bad effects”, “desire for cocaine”, “depressed”, “anxious”, “over- stimulated”, and “cocaine liking.”

VAS will be administered 30 minutes prior to the first infusion and at 5, 10, 15, 30, 45, 55, 65, 70, 75, 90, 105, 115, 125, 130, 135, 150, 165 and 180 minutes after the first infusion for screening infusion 1, and at -30, 5, 10, 15, 30, 45, 55, 65, 70, 75, 90, 105 and 120 minutes after the first infusion for baseline and treatment infusion Sessions 2 to 5. Windows for collection of VAS are nominal times  $\pm$  3 minutes for the first 30 minutes after the infusion and  $\pm$  5 minutes at all other time points.

## **6. STUDY POPULATION**

### **6.1 Full Analysis Set (FAS)**

The FAS population will include all randomized participants.

### **6.2 Safety Population**

The safety population will include all participants who are included in the FAS population and who received any study drug.

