#### **9.3.1 Infusion Session 1 (Day -2)**

For a participant to receive the first screening cocaine and saline infusions (Session 1 – Study Day -2), s/he must have a urine drug toxicology screen that is negative for drugs of abuse as listed in Exclusion #12 and alcohol. The participant's semi-supine blood pressure must be  $\leq 140$  mm Hg (systolic) and  $\leq 90$  mm Hg (diastolic), heart rate must be  $\leq 100$  beats per minute taken in the half-hour prior to receiving any cocaine infusion. If blood pressure or heart rate is elevated, it may be repeated one time to determine if the participant meets these criteria to receive an infusion. The participant's ECG taken within 30 minutes prior to receiving any cocaine infusion must not have any clinically significant abnormal arrhythmia or interval changes. The screening infusions are to ensure that participants are responsive to and safely tolerate the cocaine test doses. Only participants who are able to distinguish between a 20 mg and 40 mg dose of cocaine i.v. will be randomized. The highest score on VAS for "HIGH" effect at the 5 or 10 minute time point after cocaine infusion will be used to discriminate those individuals who can discern the differences between the two cocaine doses.

Participants who cannot safely tolerate the cocaine test doses and/or are unable to distinguish between a 20 mg and 40 mg dose of cocaine i.v. will not be eligible for the study. These participants will stay overnight for observation and be discharged from the unit the next day after their vital signs are assessed by the PI and found to be clinically stable.

Continuous cardiac monitoring by telemetry will be performed from one hour prior to starting transfusions until 4 hours after the last infusion. Participants will be monitored for at least 1 hour after the cocaine infusion by study personnel and staff. Thereafter, study personnel will monitor participants and take vital signs at the times specified in [Table 4](#).

[Table 3](#) shows the series of activities that occur on the day of the screening cocaine infusion. The times are nominal times with a window of  $\pm 3$  minutes up to 30 minutes after each infusion otherwise they are  $\pm 5$  minutes. ECG then vital signs will be collected first when multiple assessments are scheduled at the same nominal time.

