### 12.2 Study Populations

#### 12.2.1 Safety Population

The safety population will include all participants who receive any administration of study drug.

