Once a participant has been determined to be eligible, the participant will be randomized on Day -1 to receive either SXC-2023 or placebo. On Days 1 and 2, participants will receive baseline infusions of saline and cocaine (Day 1/Infusion Session 2: 20 mg cocaine; Day 2/Infusion Session 3: 40 mg cocaine). The order of the saline and cocaine infusions will be randomized for each session. The participants will receive either SXC-2023 or matched placebo once a day every morning from Days 3 to 9. On Day 8, participants will receive cocaine 20 mg infusion (Infusion Session 4) and on Day 9 participants will receive cocaine 40 mg (Infusion Session 5). Each cocaine infusion will be preceded or followed by saline i.v. infusion. The first infusion on Days 8 and 9 will begin approximately 3 hours after SXC-2023 800 mg or placebo. Each infusion will consist of a 2 mL i.v. push and will be administered 60 minutes apart. The order of the saline and cocaine infusions for each participant for Infusion Sessions 4 and 5 will be the same as the randomized order for Infusion Sessions 2 and 3, respectively. The participants will be discharged from the research clinic on Day 11, 2 days after the last infusion of cocaine (Infusion Session 5), and will have a telephone follow-up call between 7 and 10 days after clinic discharge.

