**Table 4-2 Schedule of Infusion Sessions**

Study Phase	Session Number	Study Day	Infusions (2 mL over 1 minute)
Screening	1	-2	20 mg cocaine, followed by a saline infusion, followed by 40 mg cocaine*
Baseline	2	1	Saline or 20 mg cocaine followed by either 20 mg cocaine or saline*
Baseline	3	2	Saline or 40 mg cocaine followed by either 40 mg cocaine or saline*
Treatment	4	8	Saline or 20 mg cocaine followed by either 20 mg cocaine or saline a
Treatment	5	9	Saline or 40 mg cocaine followed by either 40 mg cocaine or saline b

\* Infusions will be administered 60 minutes apart.

a The order of cocaine or saline will match the order established during Infusion Session 2 (Day 1).

b The order of cocaine or saline will match the order established during Infusion Session 3 (Day 2).

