## **7. STATISTICAL ANALYSES**

Descriptive statistics will be used to present study data. For continuous data, mean, standard deviation, median, 25th and 75th percentiles, minimum, and maximum will be presented. Categorical variables will be presented as counts and percentages. All data will be presented separately by treatment group. All data will be presented in listings, except for the assessments done to determine eligibility.

All the analyses of safety data for this study will be performed using SAS® statistical software package, version 9.4 or later. Additional software, such as R (version 4.5.1, The R foundation for Statistical Computing), may also be used for input data and TLFs generation if necessary.

Missing data will not be imputed for any analysis, except for partial dates for determining treatment emergent AEs and prior and concomitant medication (see [Section 7.1](#)). The numbers of data points reflected in summary statistics will be indicated by presenting the number of observations.

The pharmacokinetics data will be analyzed using Phoenix WinNonlin (Version 8.6 or later, Certara). Additional software such as R (version 4.3.3 or later, The R foundation for Computing) may also be used for input data and Tables, Listings, and Figures (TLFs) generation if necessary.

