## **7.3 Exposure**

The summary of study drug exposure by dose day (Day 1-9) of SXC-2023 or placebo and by cocaine infusion session (1-5) will be summarized for the safety population of descriptive statistics (counts and percentages). A listing will also be provided.

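### The SAP safety population admits only randomised participants, so people given cocaine on Day -2 and then not randomised have no place in the AE and exposure tables

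*SAP*

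**What the plan says.** SAP 6.1 sets the FAS: "The FAS population will include all randomized participants". SAP 6.2 builds the safety population on it: "The safety population will include all participants who are included in the FAS population and who received any study drug". Protocol 12.2.1 has no such condition: "The safety population will include all participants who receive any administration of study drug".

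The order of events is in SAP 4.1 and Table 4-2. Session 1, on Day -2, is "20 mg cocaine, followed by a saline infusion, followed by 40 mg cocaine". The allocation comes a day later: "Once a participant has been determined to be eligible, the participant will be randomized on Day -1 to receive either SXC-2023 or placebo". Protocol 9.3.1 and SAP 4.7.1 both make a group ineligible after that session: "Participants who cannot safely tolerate the cocaine test doses and/or are unable to distinguish between a 20 mg and 40 mg dose".

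SAP 7.4.1 presents the AE summaries for the safety population. SAP 7.3 does the same for exposure, Session 1 included: "by cocaine infusion session (1-5) will be summarized for the safety population". SAP 7 lays out all data by treatment group and says of listings: "All data will be presented in listings, except for the assessments done to determine eligibility". SAP 7.4.1 also promises listings of every AE and SAE, with no restriction to an analysis set.

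**The concern.** Session 1 is the largest planned same-day cocaine exposure in the study: up to 20 + 40 = 60 mg, against 20 or 40 mg in each of Sessions 2 to 5. The people who leave after it include those who did not tolerate it. A safety set that starts at randomisation therefore describes Session 1 only in people who came through it, and the omission is selective.

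This matters because AEs are a primary endpoint and SAP 7.4.1 plans related-event summaries for cocaine separately from SXC-2023. The study stopping criteria in SAP 4.4.1 are also not limited, as worded, to randomised people. A Session 1 reaction in someone never randomised could count towards halting enrolment and yet be in no AE table.

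**Working it through.** The plan gives no figure to reproduce. The check is of definitions against the timeline, then of scale.

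**1. Who is outside the set.** Cocaine is given on Day -2, eligibility is then decided, and randomisation is on Day -1. Anyone infused who fails Session 1 is not randomised, so is not in the FAS and cannot be in the safety population. This does not depend on how study drug is read, because FAS membership is a separate condition in SAP 6.2.

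**2. Which outputs are affected.**

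| Output | Analysis set named | People infused but not randomised |
|---|---|---|
| AE summaries (SAP 7.4.1) | Safety population | Excluded expressly |
| Exposure, Sessions 1-5 (SAP 7.3) | Safety population | Excluded expressly |
| HR, BP and ECG summaries (SAP 7.4.2) | None | No column, because of the by-treatment layout |
| Listings of all AEs and SAEs (SAP 7.4.1) | None | Should appear, without a denominator |

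**3. Whether the SAP contradicts the protocol.** This turns on *study drug*, which neither document defines.

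- Cocaine counts: the protocol synopsis lists it under its study drugs and dosing entry, and the partial-date rules in SAP 7.1 refer to an infusion of study drug.
- Cocaine does not count: the synopsis entry for the study drug names SXC-2023 alone, and Protocol 9.10 and 9.12 name study drug and cocaine as alternatives.

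On the first reading, the SAP is narrower than the protocol. On the second, people given only Session 1 are outside both safety populations, and they are missing from the same tables.

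**4. Scale.** Let f be the assumed share of infused people not randomised because they fail Session 1. To randomise 20 (SAP 4.2), number infused = 20/(1 - f) and number left out = 20f/(1 - f).

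| f (assumed) | Infused | Left out |
|---|---|---|
| 10% | 20/0.9 = 22.2 | 2.2 |
| 20% | 20/0.8 = 25.0 | 5.0 |
| 30% | 20/0.7 = 28.6 | 8.6 |
| 40% | 20/0.6 = 33.3 | 13.3 |

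Here f covers both intolerance and inability to tell the doses apart, so the last column counts exposed people, not reactions.

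**5. Whether the data exist.** Protocol 10.1 starts AE questioning at the first Day -2 infusion. Protocol Table 2 marks Day -2 AEs, vital signs and ECG for the clinical database, with no exception for people who then fail.

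**The case against.** The best case for the plan is that its objective is the interaction of SXC-2023 with cocaine, and these people never receive SXC-2023 or placebo. They are few, their events are to be listed, the reason for ineligibility is recorded (Protocol 10.17), and SAEs from admission onward are reported within 24 hours (Protocol Appendix B). The exposure table is correct for the population that it names. Most of this stands, and it is why the point is about completeness of reporting and not about validity of the comparison.

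A further point also stands. SAP 7.4.1 tabulates events that begin after the first dose of study medication, and not by session. If that means SXC-2023 or placebo, Day -2 events in randomised people are not treatment-emergent either, unless they worsen. No table of Session 1 AEs would then exist for anyone. That makes a defined Session 1 summary more useful, not less.

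A reader might go further in several ways that the documents do not support:

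- **That these people are missing from every safety output.** Only the AE and exposure tables name the safety population, and the AE and SAE listings are not limited to it.
- **That each of them received 60 mg.** Protocol 9.3.1 requires acceptable vital signs and ECG before any cocaine infusion, and 9.9 halts cocaine after a significant reaction, so 60 mg is a maximum.
- **That their Session 1 HR, BP and ECG are barred from listings.** SAP 7 exempts eligibility assessments without naming Session 1, and SAP 5.1.2 treats the same measurements as cardiovascular endpoint data. The exemption is a possible reading only.
- **That the SAP plainly contradicts the protocol.** That holds only if cocaine is a study drug.

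**Conclusion.** The point holds within these limits. People infused on Day -2 and not randomised, including any who could not tolerate the infusions, are excluded from the AE and Session 1 exposure tables and have no column in the HR, BP and ECG tables. A line listing should show their events but gives no rate.

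The documents give no Session 1 failure rate. About 2 to 13 people would be left out beside 20 randomised if the rate is 10% to 40%; that range is an assumption, and it mixes the two reasons for failure. The conflict between SAP 6.2 and Protocol 12.2.1 is conditional on the meaning of study drug, but the omission from the tables is not. The randomised comparison of SXC-2023 with placebo is unaffected, since none of these people was allocated to an arm. The change should be made, but the main analysis does not depend on it.

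**What to change.** - Define *study drug* in both documents, saying whether it includes cocaine, and reconcile Protocol 12.2.1 with SAP 6.2.
- Add to SAP 6 an all-infused set: everyone who received any cocaine infusion, randomised or not.
- For that set, report Session 1 exposure, AEs, and HR, BP and ECG maxima in one pooled column, apart from the by-arm tables.
- State in SAP 7 that Session 1 HR, BP and ECG are not covered by the exemption of eligibility assessments from listings.
- Keep the randomised set for all by-arm tables.

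The cost is SAP wording, a few extra summary tables and one listing. No new data collection is needed, provided that Day -2 data on people who fail Session 1 are entered as Protocol Table 2 indicates. No dose, schedule or clinical rule changes.
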